18.2 A. How long will the data be stored?

Response: Data and specimens storage has no expiration date and will be stored for a minimum of 7 years. The researchers may continue to rely on this for future use in research study

18.3 A. Who will have access to the data?

Response: Those physicians, nurses, and laboratory staff that are on all documentation for the study will have access to the data and specimens

18.4 A. Who is responsible for receipt or transmission of the data?

Response: Those physicians, nurses, and laboratory staff that are on all documentation for the study will have access to the data and specimens and can handle transfer of data and samples

18.5 A. How will the data be transported?

Response: All data are stored at one location and is not transported unless it is being archived. At that point files will be transferred to Iron Mountain for storage and archiving. Samples that are transported will be done so using dry ice in a properly labeled Styrofoam container by the laboratory technician.

B. Confidentiality of Study Specimens

Describe the local procedures for maintenance of confidentiality of **study specimens.**

N/A: No specimens will be collected or analyzed in this research.
(Skip to Section 19.0)

18.6 B. Where and how will all specimens be stored? Include information about: physical controls, authorization of access, and labeling of specimens, as applicable.

Response: The specimens will be stored in the CRC laboratory located at [name] and at the CTRC located in [name]. Samples will be stored in a locked -80° C freezers. Ultimately, all specimens will be transported to CTRC location for banking. Specimens will be labeled as a coded sample, using the patient's randomization number (e.g. R-12), visit time and number and sample type. Specimens will not be stored with any patient identifiable information which is kept in locked cabinets in the CRC at [name].

18.7 B. How long will the specimens be stored?

Response: Data and specimens storage has no expiration date and will be stored for a minimum of 7 years. The researchers may continue to rely on this for future use in research study

18.8 B. Who will have access to the specimens?

Response: Those physicians, nurses, and laboratory staff that are on all documentation for the study will have access to the data and specimens.

18.9 B. Who is responsible for receipt or transmission of the specimens?

Response: Those physicians, nurses, and laboratory staff that are on all documentation for the study will have access to the data and specimens and can handle transfer of data and samples

18.10 B. How will the specimens be transported?

Response: All data are stored at one location and is not transported unless it is being archived. At that point files will be transferred to Iron Mountain for storage and archiving. Samples that are transported will be done so using dry ice in a properly labeled Styrofoam container by the laboratory technician

19.0 Provisions to Monitor the Data to Ensure the Safety of Subjects

N/A: This study is not enrolling subjects, or is limited to records review procedures only. This section does not apply.

NOTE: Minimal risk studies may be required to monitor subject safety if the research procedures include procedures that present unique risks to subjects that require monitoring. Some examples include: exercising to exertion, or instruments

that elicit suicidality or substance abuse behavior. In such cases, N/A is not an acceptable response.

19.1 Describe the plan to periodically evaluate the data collected regarding both harms and benefits to determine whether subjects remain safe.

Response: The principal investigator [name], PhD and co-investigators [name] and [name] will review the data every 3 months to assess the safety of the participants. Furthermore they will also assess other risks including the physical, psychological, social, legal and economic harm to these patients. The investigators listed above will carefully watch for any invasion of privacy and breach of confidentiality. The principal investigator will be sharing the results of safety analysis of the study with the sponsor (JDRF) and to the IRB. The study groups will remain blinded. If there are any safety concerns then co-investigator [name] who is not directly involved with the patients and or in insulin titrations of the study participants will unblind the study groups on the discretion of principal investigator and the team will assess potential harm to the patients and inform the IRB and sponsor of this potential harm. The corrective actions will then be taken and research subjects will be withdrawn from the study if risks outweigh the benefits. The IRB will be kept well-informed at all times. During each patient visit, evolution of glucose levels (CGM) will be conducted to reduce the risk of hypoglycemia or hyperglycemia. After recruitment and completion of half of the target number of patients i.e. 42 patients, interim analysis will be performed to determine an overwhelming harms or benefits with one treatment option compared to another.

19.2 Describe what data are reviewed, including safety data, untoward events, and efficacy data.

Response: Patients CGM, dietary intake, BP, weight are monitored every visit to ensure safety. CGM graphs will be evaluated every visit to reduce risk of hypoglycemia or hyperglycemia. Other adverse events (including the most common side effects of nausea and vomiting, injection site allergic reaction and the rare occurrence of pancreatitis, thyroid c-cell tumors and other patient reported adverse events) will be collected.

19.3 Describe any safety endpoints.

Response: Frequency and severity of hypoglycemia.

19.4 Describe how the safety information will be collected (e.g., with case report forms, at study visits, by telephone calls with participants).

Response: The safety information will be collected at the time of the participants visit, and or during telephone calls with the participant

19.5 Describe the frequency of safety data collection.

Response: The data collection will be done at all study visits which will be at intervals of either one or two weeks depending on the number of study visit. The patients, however, will be asked to report any adverse event or safety related information via phone as soon as it occurs and it will be reviewed the same day.

19.6 Describe who will review the safety data.

Response: The principal investigator [name], PhD and co-investigators, [name] and [name] will review the data at the completion of all visits by each subject and every 3 months to assess the safety and any potential risks to the participants. Furthermore they will also assess other risks including the physical, psychological, social, legal and economic harm to these patients. The investigators listed above will carefully watch for any invasion of privacy and breach of confidentiality. The principal investigator will be sharing the results of safety analysis of the study with the sponsor (JDRF) and with the IRB. The study groups will remain blinded. If there are any safety concerns then co-investigator [name] who is not directly involved with the study participants will unblind the study groups on the discretion of principal investigator and the team will assess potential harm to the patients and inform the IRB and sponsor of this potential harm. The corrective actions will then be taken and research subjects will be withdrawn from the study if risks outweigh the benefits. The IRB will be kept well-informed at all times.

19.7 Describe the frequency or periodicity of review of cumulative safety data.

Response: Safety data will be reviewed every 3 months. Study endpoint data will be reviewed once after half of the recruited patients have completed the study and then at the end of the study

19.8 Describe the statistical tests for analyzing the safety data to determine whether harm is occurring.

Response: The statistical analysis will be carried out using student t-test, Chi-square and Wilcoxon's test for paired data

19.9 Describe any conditions that trigger an immediate suspension of the research.

Response:

- 1- New information about the safety of the used drug (Victoza) – liraglutide
- 2- Sponsor suspension of the funds.
- 3- Significant high incidence of SAE and events leading to withdrawal of subjects determined based on the continuous review by the investigators.

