Study Visit week 4: Subjects will be asked to bring in their used study pens and the pen that they are using so that study nurse can log in the amount of drug used. If needed, the dose will be increased. The goal in the first 4 weeks is to increase patient's liraglutide dose to maximum tolerated dose. Maximum dose of liraglutide will be 1.8 mg daily. Subjects experiencing mild nausea with 0.6 mg or 1.2 mg will continue at that dose in the study. Those with severe nausea/vomiting with 1.8mg will decrease their dose to 1.2 mg and continue that dose throughout the study. Blood glucose concentrations will be reviewed. Insulin dose will be adjusted if needed. CGM will be discontinued. Study drug will be dispensed to last till the next visit.

Study visit week 8: Subjects will be asked to bring in their used study pens and the pen that they are using so that study nurse can log in the amount of drug used. Blood glucose concentrations will be reviewed. Insulin dose will be adjusted if needed. Study drug will be dispensed to last till the next visit.

Study Visit week 12: Subjects will be asked to bring in their used study pens and the pen that they are using so that study nurse can log in the amount of drug used. Blood glucose concentrations will be reviewed and vascular activity will be performed. Insulin dose will be adjusted if needed. Fasting blood, research labs, HbA1c, fructosamine, lipid panel, urine pregnancy test and 24 hr urine will be collected. FMD and 24hr blood pressure will be studied. Study drug will be dispensed for additional 4 weeks.

Study Visit week 16 and 20: Subjects will be asked to bring in their used study pens and the pen that they are using so that study nurse can log in the amount of drug used. Blood glucose concentrations will be reviewed. Insulin dose will be adjusted if needed. Study drug will be dispensed for additional 4 weeks.

Study visit week 24: CGM will be inserted. They will have their body composition measured by DEXA and MRI prior to next visit.

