Response: The following data will be collected during the conduct of the study based on the study design and protocol: HbA1c, fructosamine, average glucose, percent time spent in different glycemic thresholds, standard deviations which represent the variability in blood glucose, total insulin doses (basal dose, bolus dose and total daily dose), changes in carbohydrate intake and helpings; adverse events(including the most common side effects of nausea and vomiting which is often transient occurring at the time of initiation of liraglutide and at the time of escalation of the dose and the rare occurrence of pancreatitis, thyroid c-cell tumors and other patient reported adverse events which may occur anytime) and blood pressure. The principal investigator [name], PhD and co-investigators [name] and [name] will review the data every 3 months to assess the safety of the participants. Furthermore they will also assess other risks including the physical, psychological, social, legal and economic harm to these patients. The investigators listed above will carefully watch for any invasion of privacy and breach of confidentiality. The principal investigator will be sharing the results of safety analysis of the study with the sponsor (JDRF) and to the IRB. The study groups will remain blinded. If there are any safety concerns then co-investigator [name] who is not directly involved with the patients and or in insulin titrations of the study participants will unblind the study groups on the discretion of principal investigator and the team will assess potential harm to the patients and inform the IRB and sponsor of this potential harm. The corrective actions will then be taken and research subjects will be withdrawn from the study if risks outweigh the benefits. The IRB will be kept well-informed at all times. During each patient visit, evolution of glucose levels (CGM) will be conducted to reduce the risk of hypoglycemia or hyperglycemia. After recruitment and completion of half of the target number of patients i.e. 42 patients, interim analysis will be performed to determine an overwhelming harms or benefits with one treatment option compared to another.

 10.3 List any instruments or measurement tools used to collect data (e.g. questionnaire, interview guide, validated instrument, data collection form).

Include copies of these documents with your submission.

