11.0 Study Timelines

11.1 Describe the anticipated duration needed to enroll all study subjects.

Response: 48 months

11.2 Describe the duration of an individual subject's participation in the study. Include length of study visits, and overall study follow-up time.

Response: After the screening visit, subjects who meet the inclusion and exclusion criteria, will be assigned a number and randomized to receive subcutaneous injection daily of either Liraglutide (42 subjects) or placebo (42 subjects) for 26 weeks. Total participation period will be 28 weeks including 2 weeks run in period before starting drug intervention.

11.3 Describe the estimated duration for the investigators to complete this study (i.e. all data is collected and all analyses have been completed).

Response: 60 months

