17.2 If applicable, provide a power analysis.

NOTE: This may not apply to certain types of studies, including chart/records reviews, survey studies, or observational studies. This question is asked to elicit whether the investigator has an adequate sample size to achieve the study objectives and justify a conclusion.

Response: There are no prior randomized controlled trials that have examined the effect of Liraglutide on HbA1c in subjects with type 1 diabetes. In our observational study (preliminary data), we found a decrease in HbA1c of 0.35% after 6 months of liraglutide in patients with type 1 diabetes who had a mean HbA1c of $6.45\pm0.5\%$. In our proposed study, we will include patients with HbA1c up to 8.5%. Thus we expect a greater difference in HbA1c among the two groups at the end of the study. Conservatively estimating a difference in HbA1c of 0.35% between the two groups, a sample size of 32 patients per treatment group should provide 80% power to detect a significant difference ($\alpha = 0.05$), provided the standard deviation of the residuals is not greater than 0.5. Thus 64 subjects will be needed for the study. To account for a dropout rate of 30%, we will recruit 84 subjects into the study.

17.3 Describe any procedures that will be used for quality control of collected data.

Response: Three investigators and research nurse will double check the accuracy of collected data. All laboratory testing will be standardized using references and standards.

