21.0 Risks to Subjects

21.1 List the reasonably foreseeable risks, discomforts, hazards, or inconveniences to the subjects related to their participation in the research. Consider physical, psychological, social, legal, and economic risks. Include a description of the probability, magnitude, duration, and reversibility of the risks.

NOTE: Breach of confidentiality is always a risk for identifiable subject data.

Response:

Subjects who experience severe nausea or vomiting after starting liraglutide will discontinue the study. Those with mild or moderate nausea will continue for at least one more week. If they continue to experience significant nausea (defined as interfering with normal activities), they will discontinue the study.

Subjects who develop pancreatitis will be withdrawn from the study.

Subjects who develop a new thyroid tumor during the study will be withdrawn. Patients will be informed that they should let study investigators know if they develop any swelling in the neck.

For the entire duration of the study, the patients will maintain a diary to record any hypoglycemia and other untoward side effects like nausea, changes in appetite and other experiences. Patients will be instructed to call the Diabetes Center to speak to a study investigator directly in case of any problem or untoward side effects. They will be specifically asked to call if they have hypoglycemia (blood sugar <70 mg/dl) or hyperglycemia (blood sugar >250 mg/dl) on more than one occasion. The target blood glucose during the study will be between 70-180mg/dl at all times, without increasing the incidence of blood glucose < 70 mg/dl.

The following Information from the boxed warning in the package insert regarding the risk of thyroid c-cell tumors will be discussed in details with all participating subjects:

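### The safety endpoint, hypoglycaemia frequency, is undefined and no listed safety test accounts for time at risk, so hypoglycaemia on liraglutide can be understated if those patients leave earlier

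*Combined protocol and SAP*

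**What the plan says.** Section 19.3 gives the safety endpoint in full as "Frequency and severity of hypoglycemia". It does not say whether frequency means a count, the proportion of patients with an event, or a rate. Section 21.1 describes the recording: "the patients will maintain a diary to record any hypoglycemia", throughout the study. Section 19.8, which asks how harm will be tested for, answers "The statistical analysis will be carried out using student t-test, Chi-square" and adds a Wilcoxon test for paired data. No event rate, person-time denominator or exposure adjustment appears anywhere in the document.

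Follow-up will not be equal for all patients. Section 11.2 plans liraglutide ("42 subjects) or placebo (42 subjects) for 26 weeks"), and Section 17.2 sizes the trial "To account for a dropout rate of 30" per cent, with no split by arm and no timing. Section 10.1 removes patients with severe nausea or vomiting at week 1, and those with significant nausea on the lowest dose at week 2. Section 21.1 has a similar rule, tied to starting liraglutide. Section 20.1 makes severe and frequent hypoglycaemia itself a reason for withdrawal. Under Sections 20.2 and 20.3, a patient who withdraws completely contributes only what was recorded before leaving.

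**The concern.** A patient observed for two weeks has far less opportunity to record an event than one observed for 26. If one arm loses more patients, or loses them sooner, its mean event count falls even when the underlying rate is the same. The proportion with at least one event falls too, so moving from the t-test to chi-square does not avoid the problem. Section 10.2 describes nausea and vomiting as the most common side effects, occurring when liraglutide is started and when its dose is raised. Earlier loss on liraglutide is therefore a reasonable expectation, and the error would then favour the active arm.

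The paired Wilcoxon test compares a patient with himself or herself within one arm. It cannot show excess harm against placebo.

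At stake is the between-arm comparison meant to show whether harm is occurring. The interim look after 42 completed patients (Sections 10.2 and 19.1) is meant to detect overwhelming harm, and the plan names no other tests of harm for it. The primary HbA1c analysis is not affected.

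**Working it through.** The documents give no figure for the safety analysis, so there is none to reproduce. The check is how far the listed comparisons move when time at risk differs between arms.

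**Inputs from the documents.** Planned follow-up is 26 weeks with 42 patients per arm (Section 11.2). Overall dropout is 30% (Section 17.2); with equal allocation this is the plain average of the two arms' dropout.

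**Assumed.** Dropout d in each arm, week of leaving t, and an event rate that is the same in both arms and constant over time.

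**Formula.** Mean weeks observed = (1 − d) × 26 + d × t. With equal true rates, the ratio of mean counts per patient equals the ratio of mean weeks observed.

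| Dropout, liraglutide vs placebo | Week of leaving | Overall dropout | Liraglutide weeks | Placebo weeks | Apparent ratio |
|---|---|---|---|---|---|
| 30% vs 30% | 2 and 2 | 30% | 0.7×26 + 0.3×2 = 18.8 | 18.8 | 1.00 |
| 20% vs 10% | 2 and 2 | 15% | 0.8×26 + 0.2×2 = 21.2 | 0.9×26 + 0.1×2 = 23.6 | 0.90 |
| 30% vs 10% | 2 and 2 | 20% | 18.8 | 23.6 | 0.80 |
| 30% vs 30% | 2 and 13 | 30% | 18.8 | 0.7×26 + 0.3×13 = 22.1 | 0.85 |
| 40% vs 20% | 2 and 13 | 30% | 0.6×26 + 0.4×2 = 16.4 | 0.8×26 + 0.2×13 = 23.4 | 0.70 |

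The first, fourth and fifth rows keep the protocol's overall 30%. In the last row a true rate ratio of 1.5 would appear as 1.5 × 0.70 = 1.05, which is close to no difference.

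**Any-event proportion.** For a constant weekly rate λ with Poisson events, the proportion with at least one event is (1 − d)(1 − e^(−26λ)) + d(1 − e^(−tλ)). Take λ = 0.1 (assumed) and the last row of the table:
- liraglutide: 0.6 × 0.926 + 0.4 × 0.181 = 62.8%
- placebo: 0.8 × 0.926 + 0.2 × 0.727 = 88.6%
- ratio: 0.71, although the true rates are equal.

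**Does dividing by time repair it?** With a constant rate, yes: each row returns to 1.00. If events cluster early, a simple person-time ratio overshoots slightly. Suppose the rate in weeks 0–4 is three times the later rate in both arms. In units of the later weekly rate, expected events are 3×4 + 22 = 34 by week 26, 3×4 + 9 = 21 by week 13, and 3×2 = 6 by week 2. In the last row of the table:
- liraglutide: 0.6×34 + 0.4×6 = 22.8 events over 16.4 weeks = 1.390 per week
- placebo: 0.8×34 + 0.2×21 = 31.4 events over 23.4 weeks = 1.342 per week
- person-time ratio 1.04, against a raw count ratio of 22.8/31.4 = 0.73.

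With a fivefold early rate and 45% against 15% dropout, the person-time ratio is 1.09 and the raw count ratio 0.69. Person-time is imperfect but much nearer to 1.00.

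**The case against.** Two stronger readings are tempting. One is that the plan analyses raw event counts; the other is that its analysis will make hypoglycaemia look rarer on liraglutide. The documents support neither. Because frequency is undefined, a t-test on each patient's events per week would be consistent with the text and would already use time at risk. No arm-specific dropout or timing is given, and with equal dropout and timing there is no bias. The trial is double blind, so the nausea rules bind both arms. Section 10.1 also keeps many intolerant patients in the study on the same or a lower dose, whereas Section 21.1 reads more strictly. Those two passages must be reconciled, because they bear on how many patients leave early. All of this stands, and it makes the point conditional.

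It can also be said that hypoglycaemia is already compared on a normalised scale. Section 10.2 collects "percent time spent in different glycemic thresholds", and Section 17.1 compares time below 70 and below 40 mg/dl between groups. That helps only in part. These are secondary efficacy measures, not the Section 19.3 endpoint. In the Section 10.1 schedule, at week 4 "CGM will be discontinued", and it is reinserted only at week 24, so most of follow-up is uncovered apart from patients who use their own device. Sections 10.3 and 19.2 speak of CGM review at every visit, which does not fit that schedule. On either reading, patients who have left give no later readings. Three-monthly review and same-day review of telephoned events protect individuals, but they are not a comparison of arms.

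Finally, an offset assumes that leaving is unrelated to a patient's event rate. Section 20.1 makes hypoglycaemia a withdrawal reason, so that assumption is doubtful. This stands as a limitation of the remedy, but it does not favour ignoring exposure.

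**Conclusion.** The point holds in conditional form. Sections 19.3 and 19.8 leave the safety endpoint undefined and list tests that, as stated, take no account of time at risk; one of them does not compare arms. If liraglutide patients leave earlier, comparisons of counts or of any-event proportions can understate hypoglycaemia on liraglutide. In the illustrations the apparent count ratio under equal true rates runs from 1.00 (no bias) to 0.70. Every value below 1.00 depends on assumed arm-specific dropout and timing, which the documents do not give. The withdrawal rules make such a difference foreseeable, not certain. The change is worth making before the data are examined, because it costs little and does no harm if exposure turns out equal.

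**What to change.** - In Section 19.3, define frequency as hypoglycaemic events per patient-week on study.
- In Section 19.8, make the between-arm comparison a negative binomial regression with log time on study as offset.
- Report follow-up time and withdrawal reasons by arm.
- Report the number of patients with any severe event by arm alongside their exposure. An exact test on that proportion would ignore time at risk just as chi-square does.
- Keep the paired Wilcoxon test only as a within-arm description, not as evidence of harm against placebo.
- State as a limitation that the offset does not fully correct for withdrawal caused by hypoglycaemia, or for event rates that change during titration. The simple person-time ratio may reach about 1.04 to 1.09 under equal true rates if events cluster early.

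The cost is a few lines in Sections 19.3 and 19.8 and slightly more analysis work. The diary supplies the events and the visit schedule the time on study, so no new assessment is needed.
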